3.1.1 Considerations Due to the COVID-19 Pandemic

Due to the COVID-19 pandemic, adjustments to the visit location/method or schedule may be made during the long-term follow-up to accommodate safety concerns and restrictions experienced by individual subjects and sites. In all cases, subjects will be kept informed, via site staff, as much as possible, of changes to the study and monitoring plans that could impact them.

Discontinuation of subjects from the study post-treatment with AMT-061 is not considered to be in the best interest of the subject, due to the irreversible nature of the IMP. Wherever possible,

every effort is to be made to have the subject visit the clinic for the study visits according to schedule. Should a clinic visit not be possible, options that may be considered include site nurses travelling to a subject's home, local laboratory use, or home nursing services (for certain visits, if pre-approved by the Investigator and Sponsor). These options, if used, will be supplemented with a phone call or telemedicine/telehealth safety follow-up call. A (temporary) transfer of a subject to an alternate clinical trial site may also be considered in order to continue on-site visits, only if this does not pose undue burden to the subject and/or "new" site.

In some instances, it may not be possible to conduct any type of visit at all. Where none of the above options are feasible, subject visits may be moved beyond the maximum visit window permitted. Such delays will be assessed on a case by case basis. Until visits are rescheduled, supplemental phone calls or telemedicine/telehealth contact between Investigator/study staff and subject are to be arranged.

Supplemental phone calls or telemedicine/telehealth safety follow-up calls will be used to confirm the subject's status and wellbeing. At these calls, safety information should be gathered (i.e., AEs, concomitant medication use), subjects should be asked about any new unreported bleeds or factor IX consumption and confirm their use of the paper diaries (as applicable), and there should be continued discussions with the subject on the importance of a healthy liver. These discussions will be documented in the source documents.

All deviations from the study protocol are to be documented, with rationale. If a protocol deviation is due to the COVID-19 pandemic, this will be noted.

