6.2.3.12 Other Safety Laboratory Evaluations

All clinical laboratory assays will be performed according to the laboratory's normal procedures. Reference ranges are supplied by the laboratory and used to assess the clinical laboratory data for clinical significance and out-of-range pathological changes. The Investigator should assess outof-range clinical laboratory values for clinical significance, indicating if the value(s) is/are not clinically significant or clinically significant. Abnormal clinical laboratory values, which are unexpected or not explained by the subject's clinical condition may be, at the discretion of the Investigator or Sponsor, repeated until confirmed, explained, or resolved as soon as possible.

The safety laboratory assessments that will be performed at the central and/or local laboratory are specified in Table 8, and as indicated in the schedule of events (Table 2 and Table 4).

Central Laboratory		
Serum Chemistry	Serum electrolytes (sodium, potassium), creatinine, creatine kinase, gamma-	
	glutamyltransferase, AST, ALT, ALP, CRP, albumin, total bilirubin, glucose (non-	
	fasting)	
Hematology	Hemoglobin, hematocrit, platelet count, red blood cells, white blood cells with	
	differential count, CD4+ count (all expressed in % as well as in absolute numbers)	
Coagulation	aPTT, PT (or INR [International Normalized Ratio])	
Serology	HIV viral load, HBsAg, HBeAg, HBV DNA and HCV RNA	
Alpha-fetoprotein	AFP	
Local Laboratory	AST and ALT	

 Table 8 Safety Laboratory Parameters Assessed at the Central and/or Local Laboratory

Abbreviations: AFP: alpha-fetoprotein; ALP: alkaline phosphatase; ALT: alanine aminotransferase; aPTT: activated partial thromboplastin time; AST: aspartate aminotransferase; CRP: c-reactive protein; DNA: deoxyribonucleic acid; HbeAg: hepatitis B extracellular antigen; HBsAg: hepatitis B surface antigen; HBV: hepatitis B virus; HCB: hepatitis C virus; HIV: human immunodeficiency virus; RNA: ribonucleic acid.

The Investigator should attempt to arrange with the local laboratory that analysis results are provided on the same day, or the day after, blood sampling has taken place. Local laboratory results should be provided as soon as possible to the Investigator.

The Investigator should enter analysis results, as well as related reference ranges and analysis method applied (if applicable) in the eCRF. In addition, the local laboratory result reports should be kept in the subject's medical record.

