completed for the Month 24, Month 36, Month 48, and	Section 6.2.2.4
Month 60 visits during the Long-term Follow-up Phase, if	
those visits are impacted by COVID-19. Adjustments to the	
visit timing within the allowed visit window are to be	
documented.	
Local laboratory assessments of factor IX (one-stage aPTT	Table 4
for factor IX activity) and transaminases (AST/ALT) for	Section 6.2.3.12
local monitoring were added to the long-term follow-up	Section 6.2.5
activities (starting at Month 30 as all subjects were	
approaching this visit at the time of the protocol	
amendment).	
Reference to the schedule of events for laboratory	
parameters (Table 2 and Table 4) was added to the following	
sections, for clarity on the timing of these assessments	
during the study:	
Section 6.2.3.12 (Other Safety Laboratory Evaluations)	
Section 6.2.5 (General Information Regarding Laboratory	
Sampling and Results).	~
Section 1.6 "Accommodations Due to the COVID-19	Section 1.6 (new)
Pandemic" was added as an introduction to the COVID-19	
pandemic and its impact on clinical trial procedures.	
Section 3.1.1 "Considerations due to the COVID-19	Section 3.1.1 (new)
Pandemic" was added to discuss potential adjustments to the	
meeting schedule or visit location/method due to the	
COVID-19 pandemic and to indicate that all deviations from	
the protocol due to the pandemic are to be documented.	
Recommendations on use of antithrombotic treatment was	Section 5.6.2, 5.6.3
added for subjects with factor IX activity in the	Section 6.2.2.1
non-hemophilic ($\geq 40\%$ of normal) range and with a	
confirmed COVID-19 infection.	
L	

	1
Additional clarification and recommendations on	Section 5.6.4
transaminase elevation management was added including	
discussions on corticosteroid tapering, considerations with	
prolonged high dose corticosteroid use, and considerations	
with potential and confirmed COVID-19 infections.	
Addition of phrase indicating that the 5 years of follow-up	Section 6.1.4
after administration of AMT-061 is in line with the FDA	
guidance on long-term follow-up after administration of	
human gene therapy products.	
Removal of use of international criteria for assessment of	Section 7.3.1
laboratory value abnormalities.	
To align with the eCRFs, the possible options for causality	Section 7.3.2
assessments for AEs were updated, with options being	
related, possibly related, unlikely related, and not related.	
Clarification that trial monitor visits may be virtual.	Section 8.1

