1. INTRODUCTION

This Statistical Analysis Plan (SAP) outlines the statistical methods for the display, summary and analysis of data for the uniQure Study CT-AMT-061-01. The SAP should be read in conjunction with the study protocol. This version of the SAP has been developed using the CT-AMT-061-01 Protocol (Version 3.0 dated 10 Feb 2021) and the CT-AMT-061-01 CRF (Revision 13.0 dated 02 Apr 2020).

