- An unplanned assessment will be assigned to a scheduled visit only if that visit has a missing value for the relevant endpoint and the visit was a scheduled time point for the performance of the assessment per the study protocol.
- Analysis windows for the assignment of unplanned assessments will range from the previous visit at which the endpoint is planned to be collected to the next visit at which the endpoint is planned to be collected.
- The unplanned assessment closest in time within the analysis window (either before or after) will be used to replace a missing assessment for a scheduled visit. If two unplanned

assessments are both the closest in time, with one being before and the other being after, the earlier assessment will be used.

- For visit-based efficacy endpoints, values obtained before the post prophylaxis period will not be candidates to be used for imputing missing values for post-treatment visits that are during the post prophylaxis period.
- For all visit-based endpoints, values obtained prior to treatment will not be used for imputing missing values for post-treatment-period planned assessments.
- Only values from unplanned assessments (not planned assessments) will be used to replace a missing scheduled assessment.
- An unplanned assessment may be used more than once provided it lie within the analysis window for two consecutive scheduled time points at which the assessment was not performed as planned.

For factor IX activity and factor IX protein, only central-laboratory unplanned-assessment values will be candidates for assignment to a scheduled visit that has no central-laboratory value.

An exception to the above windowing rules is that Vital Signs will have values assigned to analysis visits according to the visit windows given in Table 6 (Analysis Study Time Windows for Vital Signs Assessments).

Any other rules for missing data handling will be given in the endpoint-specific sections.

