- When numbers with decimal points are included in brackets (e.g., percentages), have the brackets aligned to the right and then padded to allow for all possible percentages and then the left brackets will also be aligned. For example:

AMT-061 (AAV5-hFIXco-Padua)
Trial ID: CT-AMT-061-01

Version 3.0
16 Jun 2021
Page 5 of 156

Brackets Align

(99.9%) (xx.x%)
(9.9%) (x.x%)

- It is recommended that all column entries in a summary tables and listings are aligned to the center.
- Columns for text fields are all left justified. Columns with whole numbers are all right justified.
- For graphs, the lines are distinguishable and that the symbols for each line are appropriate. Legend is consistent across output for Treatment names and abbreviations.

Use of N versus n

- N = total number of subjects in the defined analysis set.
- n = total number of subjects in the specific category.
- If N is specified in the column heading then any reference to the number of subjects in the body should be small n, as shown in the following example:

Demographic Parameter	Treatment Group A (N=xxx)	Treatment Group B (N=xxx)	Total (N=xxx)
Age (years)			
n	xxx	xxx	xxx
Mean	xx.x	xx.x	xx.x
SD	x.x	x.x	x.x
Median	xx.x	xx.x	xx.x
Minimum, Maximum	xx, xx	xx, xx	xx, xx

A Note for Subject Data Listings

- Observed Dates/AE Severity/Relationship to investigational product is used in subject data listings.
- Observed values or raw assessment scores are used in data listings along with their derived values used in analyses, e.g., raw assessment scores and derived total scores.
- If a full date is not available, please use the available partial date.
- If there are no observations that qualify for a listing please output the following: “No observations qualify for this listing”
- Only central laboratory results will be presented except for aPTT FIX activity results and local ALT/AST values.

Data Handling Rules

Here are some additional data handling rules for FIX (factor nine) therapies to help calculate total annualized FIX therapy rates.

For start dates having a missing day (but with non-missing month), the start date will be imputed as the 15th of the month, unless this imputation would make the start date to be on or subsequent to the end date.

For start dates having a missing day (but with non-missing month), end date will be imputed as the 15th of the month, unless this imputation would make the start date to be on or prior to the start date.

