[a] Baseline is the last available measurement prior to IMP administration.

NA: Not Applicable.

Unscheduled visits that could not be assigned to a scheduled visit are not included. If there were multiple values for a visit, the last value was chosen for the analysis.

Source: Listing 4.5.2

Report generated by program: PPD

Version yyyy-mm-dd xx:xx

(Page n of N)

Note to Programmer: Repeat for all remaining visits according to “Table 3 Analysis Study Time Window for Clinical Lab Assessments in the SAP.” Repeat the parameter at the beginning of each page under column header. Repeat for all continuous laboratory variables. Sort by parameter and visit. The table is to be based on central laboratory values.

The decimal precision in the mock table above is shown only as a placeholder and is not necessarily the right precision for any specific parameter. The needed decimal precision can vary across safety lab parameters (even within a class such as hematology, serum chemistry, or coagulation). In general, give the Maximum and Minimum the maximum number of decimal places that any value for the parameter has. Once the decimal precision for display for the Maximum and Minimum of a given parameter is established, then simply follow the rules (given near the beginning of this document) for decimal display of various statistics relative to the established decimal precision for the Minimum and Maximum.

AMT-061 (AAV5-hFIXco-Padua)
Trial ID: CT-AMT-061-01

Version 3.0
16 Jun 2021
Page 48 of 156

Table 3.2.2 Central Laboratory Parameters by Visit and Time of Assessment – Serum Chemistry
Analysis Set: All Subjects Treated

Source: Listing 4.5.3

Note to Programmer: Similar layout to [table 3.2.1](#)

Table 3.2.3 Central Laboratory Parameters by Visit and Time of Assessment – Coagulation
Analysis Set: All Subjects Treated

Source: Listing 4.5.4

Note to Programmer: Similar layout to [table 3.2.1](#)

Table 3.2.4 Central Laboratory Parameters by Visit and Time of Assessment – Serology
 Analysis Set: All Subjects Treated

Parameter (unit)	Visit	Statistics	Actual Value
Continuous Parameter 1 (unit)	Baseline [a]	n	xxx
		Mean (SD)	x.xxx (x.xxx)
		Median	x.xxx
		Minimum, Maximum	x.xx, x.xx
	xxx	n	xxx
		Mean (SD)	x.xxx (x.xxx)
		Median	x.xxx
		Minimum, Maximum	x.xx, x.xx
	xxx	n	xxx
		Mean (SD)	x.xxx (x.xxx)
		Median	x.xxx
		Minimum, Maximum	x.xx, x.xx
...			

AMT-061 (AAV5-hFIXco-Padua)
 Trial ID: CT-AMT-061-01

Version 3.0
 16 Jun 2021
 Page 50 of 156

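### If haematology, chemistry, coagulation or AFP are tested locally under Protocol 3.1.1, the SAP's central-only output rule leaves those results out of its laboratory listings and tables

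*Protocol*

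**What the plan says.** Protocol 3.1.1 states that, because of the pandemic, "adjustments to the visit location/method or schedule may be made during the long-term follow-up". Where a clinic visit is not possible, the options include "local laboratory use, or home nursing services (for certain visits, if pre-approved by the Investigator and Sponsor"). The section names no analytes and does not say whether local use means testing or only sampling.

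The note on subject data listings in SAP Appendix 5 reads: "Only central laboratory results will be presented except for aPTT FIX activity results and local ALT/AST values". The programmer note to Table 3.2.1 (haematology) adds: "The table is to be based on central laboratory values". The COVID-19 windowing rules in SAP 6.3 restrict laboratory source for two analytes only: "For factor IX activity and factor IX protein, only central-laboratory unplanned-assessment values will be candidates" to fill a scheduled visit.

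On data capture for local results, Protocol 6.2.3.12 says: "The Investigator should enter analysis results, as well as related reference ranges and analysis method applied (if applicable) in the eCRF".

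The SAP does not predate the contingency. Its introduction says: "This version of the SAP has been developed using the CT-AMT-061-01 Protocol (Version 3.0 dated 10 Feb 2021"). The protocol's amendment history marks the pandemic section, in that same version, as "Section 3.1.1 (new").

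**The concern.** The protocol opens a local route for laboratory data in long-term follow-up, and the SAP's outputs have no matching entry except for factor IX activity and ALT/AST. A locally tested bilirubin, creatinine, platelet count or AFP could therefore exist and still look missing in the report.

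Haematology, serum chemistry and AFP are stated safety objectives (Protocol 2.3) for an irreversible treatment given to three subjects. Visits are six months apart, so each result carries weight. A local bilirubin above 2 × ULN, or platelets below 50 × 10⁹/L, would not be counted as PCS. It would surface only if the investigator judged it clinically significant and recorded an adverse event. The CSR addenda must also describe information missing because of COVID-19 (Protocol 9.3), and that account would be wrong if a result existed but was not shown.

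**Working it through.** No sample size, power or error-rate figure is involved. The check traces each safety-laboratory output to its data source, then counts visits.

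**Step 1: where could a local result appear?**

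| SAP output | Source | Basis |
|---|---|---|
| Listings 4.5.2 to 4.5.6 (haematology, chemistry, coagulation, serology, AFP) | Central | Titles name Medpace, which SAP 6.8.4 identifies as the central laboratory; Appendix 5 listing rule |
| Tables 3.2.1 to 3.2.3 | Central | Titles; note to 3.2.1, whose layout 3.2.2 and 3.2.3 follow |
| Tables 3.2.4 (serology) and 3.2.8 (haematology shifts) | Local values barred | Programmer notes; 3.2.9 (chemistry shifts) follows the layout of 3.2.8 |
| Table 3.2.5 (AFP) | Central, by inference | No bar in the shell; its source is Listing 4.5.6 |
| Table 3.2.7 and Listing 4.5.7 (PCS) | Central, by inference | No bar in the Table 3.2.7 shell; SAP Table 4 puts these criteria under its central heading, and its local block holds only AST and ALT |
| Table 3.2.6 and Listing 4.5.1 | Local AST/ALT | The only safety-laboratory outputs that take local values |

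**Step 2: does this agree with the rest of the plan?**

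- SAP 5.1 puts all available data on treated subjects into every presentation, and SAP 6.1 says much the same. The Appendix 5 rule is narrower.
- The protocol synopsis gives central values priority when both sources have a result; Section 9.9 repeats this for efficacy. Neither discards a result that exists only locally.
- SAP 7, on departures from the protocol, mentions only the factor IX contamination rule.
- SAP 6.8.4 flags high and low values against the range of whichever laboratory produced them, so the SAP text can already accommodate a local result.

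**Step 3: how many visits?**

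- Long-term visits: Months 18, 24, 30, 36, 42, 48, 54 and 60, so 8 × 3 subjects = 24 subject-visits.
- Section 3.1.1 arrived with Version 3.0 (10 Feb 2021). The amendment history says all subjects were then approaching Month 30. That leaves Months 30 to 60: 6 × 3 = 18.
- The documents do not give the number affected. Range: 0 to 18.
- One local-only visit takes that visit's n from 3 to 2 (1/3 = 33% lost). The subject's gap between central values becomes 6 + 6 = 12 months, unless an additional visit supplies a central value.

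**Step 4: which analytes have a PCS criterion that a local value could meet?**

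- Absolute limit or multiple of ULN (SAP Table 4): potassium, creatinine, ALP, total bilirubin, low haemoglobin, platelets, white cells.
- Relative to baseline: the haemoglobin-rise criterion, which would compare a local value with a central baseline.
- No criterion: AFP, GGT, aPTT, PT. For these the only loss is from listings and by-visit tables.

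**The case against.** The strongest reply is that local use was never meant to extend to these analytes. Protocol 6.2.5 sends everything to the central laboratory except factor IX activity, factor IX inhibitors and AST/ALT. Table 8 puts AFP, chemistry, haematology and coagulation under the central heading. The amendment that created 3.1.1 also added local factor IX activity and AST/ALT from Month 30, and those are the two exceptions in the Appendix 5 rule. On that reading the documents agree. This stands as a plausible reading, but 3.1.1 does not say it. Since those two tests were already scheduled locally at every visit from Month 30, offering local laboratory use as a contingency may well mean something wider.

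A reader might infer that such results are certain to be in the database. The documents do not show this: the eCRF sentence in 6.2.3.12 follows Table 8, where local means AST and ALT only.

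A reader might also infer that every laboratory table expressly bars local values. That is too strong. Tables 3.2.5 and 3.2.7 carry no such note, and the Appendix 5 rule stands under a heading about listings. The shells for the laboratory listings are not in the public document, so only their titles can be checked.

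Safeguards exist: adverse event reporting, additional visits for missed measurements (Protocol 6.1.5), assignment of unplanned values to missed visits (SAP 6.3) and a listing of missed visits. They reduce the harm. None of them presents a local result that the investigator considers not clinically significant.

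**Conclusion.** The point holds conditionally and should be corrected. If haematology, chemistry, coagulation or AFP were tested locally under 3.1.1, the results would be left out of the laboratory listings and the by-visit and shift tables. By inference from SAP Table 4 and the source listings, they would also be left out of the PCS and AFP tables. This is a stated rule in conflict with SAP 5.1 and stricter than the protocol's priority for central values.

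The size is at most about 18 subject-visits and possibly none. A count of 24 would include Months 18 and 24, which fell before the provision existed. The conclusion assumes that local laboratory use can mean local testing; if samples were only drawn locally and shipped, nothing is lost. The documents do not support saying that safety data have been or will be lost. No efficacy endpoint is affected.

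**What to change.** Amend the Appendix 5 listing rule so that results obtained only from a local laboratory under Protocol 3.1.1 are listed, flagged by laboratory source and shown with that laboratory's reference range. Count them, flagged, in Table 3.2.7 and Listing 4.5.7 where the criterion is an absolute limit or a multiple of ULN. For AFP, GGT and the coagulation tests the gain is the listing alone. Keep by-visit summaries, changes from baseline and shift tables central-only. Confirm that the eCRF can hold these results with units and ranges. SAP 6.9 repeats the same analyses for the Month 60 addendum, so the change would carry through to it.

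The cost is a short SAP revision, a small programming change and possibly a small eCRF addition. The drawback is mixed assays in the flagged outputs, which the source flag and local range make visible. If no local testing of these analytes takes place, nothing changes.

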3.2 Trial Design Rationale

In gene therapy it is common practice to provide a single dose of vector via IV infusion. This infusion in a previous trial with AMT-060 was proven to be safe and effective resulting in identification of a clincial dose for AMT-060 to proceed to further clinical studies. Although this resulted in successful conversion of clinical phenotype to mild in most subjects, the desired goal is to achieve higher levels of factor IX activity to allow for a more consistent and meaningful clinical response. This trial will investigate AMT-061 at the identified dose for AMT-060 ($2 \times 10^{13} \text{ gc/kg}$).

This is the first trial with the gene product AMT-061 in humans. As AMT-061 is an isolated modification of the wild-type human factor IX in AMT-060, it is expected that the safety of this product improvement will be similar as the safety characteristics that have been described for AMT-060 at a dose of 2×10^{13} gc/kg. Also, clinical benefit of AMT-060 was achieved at this dose (refer also to Section 1.4 for a description of the Phase 1/2 trial). Therefore, a similar dose of AMT-061 will be used in this trial. Based on NHP studies with AMT-061, as well as data from patients with the natural Padua mutation, it is expected that the modified product AMT-061 will lead to a higher level of circulating factor IX activity at comparable levels of factor IX protein and thereby increase the likelihood of alleviating the need for exogenous therapy,

including the need for on-demand treatment of traumatic bleeds and selective prevention of a bleed (e.g., because of upcoming physical activity, sports, etc.). At $2 \ge 10^{13}$ gc/kg, AMT-061 is expected to result in mean factor IX activity ranges of 40% of normal, ranging between approximately 18-76%.

This trial is conducted at multiple centers as the prevalence of severe and moderately severe hemophilia B subjects is low.

Due to the nature of the disease in question it is not ethical to perform a placebo-controlled trial and no relevant active comparators exist. Based on this the trial is designed as an open-label and uncontrolled trial.

